Patients with a past history of malignant tumour	Patients with a past history that falls under the category of MedDRA SMQ Code 20000194 (SMQ Malignant tumours [Scope: Narrow]) (If “No concurrent illness existed at the initiation of treatment with Adcetris” is selected in the field of “Past history/concurrent illness of malignant tumours” in the case report form, the pulmonary disorder should be regarded as a past history.)
Patients with concurrent malignant tumour	Patients with a concurrent illness that falls under the category of MedDRA SMQ Code 20000194 (SMQ Malignant tumours [Scope: Narrow]) (If “A concurrent illness existed at the initiation of treatment with Adcetris” is selected in the field of “Past history/concurrent illness of malignant tumours” in the case report form, the pulmonary disorder should be as a concurrent illness.)
Patients with concurrent diabetes mellitus	Patients with a concurrent illness that falls under the category of MedDRA SMQ Code 20000041 (SMQ Hyperglycaemia/new onset diabetes mellitus [Scope: Narrow])
Patients with hypertension	Patients with a concurrent illness that falls under the category of MedDRA SMQ Code 20000147 (SMQ Hypertension [Scope: Narrow])
Patients with concurrent dyslipidaemia	Patients with a concurrent illness that falls under the category of MedDRA SMQ Code 20000026 (SMQ Dyslipidaemia [Scope: Narrow])
Patients with concurrent hyperuricaemia	Patients with a concurrent illness that falls under the category of MedDRA PT Code 10020903 (Hyperuricaemia)
Patients with concurrent infection	Patients with a concurrent illness that falls under the category of MedDRA SOC Code 10021881 (Infections and infestations)
Patients with concurrent peripheral neuropathy	Patients with a concurrent illness that falls under the category of SMQ Code 20000034 (SMQ Peripheral neuropathy [Scope: Narrow])
Patients with other concurrent illnesses	Patients with any concurrent illness other than those listed above
Antibiotics/synthetic antibacterial agents	Drugs with the first three digits of YJ Code being either one of 611 to 616, 619, or 624 that are entered in the field of “Drugs used for the prevention of infection” (If more than one antibiotics/synthetic antibacterial agents are used in the same patient, it will be counted as one patient.)
Antifungals	Drugs with the first three digits of YJ Code being 617 or the first seven

Term	Definition

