	digits being 6290002 or 6290004 that are entered in the field of “Drugs used for the prevention of infection” (If more than one antifungals are used in the same patient, it will be counted as one patient.)
Antivirals	Drugs with the first three digits of YJ Code being 625 that are entered in the field of “Drugs used for the prevention of infection” (If more than one antivirals are used in the same patient, it will be counted as one patient.)
Trimethoprim-sulfamethoxazole combinations	Drugs with YJ Code being 62901000 that are entered in the field of “Drugs used for the prevention of infection” (If more than one trimethoprim-sulfamethoxazole combinations are used in the same patient, it will be counted as one patient.)
Other prophylactics against infections	Any drug entered in the field of “Drugs used for the prevention of infection” other than prophylactics against infections listed above (If more than one other prophylactics against infections are used in the same patient, it will be counted as one patient.)
Peripheral sensory neuropathy (as an adverse event)	Adverse events with “Sensory neuropathy” entered in the “Category of peripheral nerve disorders” in the field of “Adverse events: [1] Peripheral nerve disorders] in the case report form. MedDRA PT Code 10034620 should be assigned regardless of data entered in “Symptoms” in the field.
Peripheral motor neuropathy (as an adverse event)	Adverse events with “Motor neuropathy” entered in the “Category of peripheral nerve disorders” in the field of “Adverse events: [1] Peripheral nerve disorders] in the case report form. MedDRA PT Code 10034580 should be assigned regardless of data entered in “Symptoms” in the field.
Peripheral neuropathy (as an adverse event)	Adverse events with “Other” entered in the “Category of peripheral nerve disorders” in the field of “Adverse events: [1] Peripheral nerve disorders] in the case report form. MedDRA PT Code 10029331 should be assigned, regardless of data entered in “Symptoms” in the field.
Pulmonary disorders (as adverse events)	Adverse events that fall under the category of Appendix “Definition of Pulmonary Disorders”
Infusion reaction (as an adverse event)	MedDRA PT Code 10051792 (Infusion related reaction) will be assigned, regardless of symptoms entered in the field of “Adverse events: [4] Infusion reaction.”

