5.0 Safety Analysis

5.1 Occurrences of adverse events and adverse drug reactions/infections

5.1.1 Occurrence of adverse events

(1) Analysis sets to be used

Safety analysis set, safety analysis set (Hodgkin’s lymphoma), and safety analysis set (anaplastic large-cell lymphoma)

(2) Data to be analyzed

Data listed below will be analyzed.

For data entered in the field of “Adverse events: [1] Peripheral nerve disorders] in the case report form, MedDRA PT Code for peripheral sensory neuropathy, peripheral motor neuropathy, or peripheral neuropathy should be assigned, regardless of data entered in “Symptoms” field (see Section 1.2, the same applies hereinafter).

MedDRA PT Code for “Infusion related reaction” should be assigned to the field of “Adverse events: [4] Infusion reaction” in the case report form, regardless of data entered in “Symptoms” field (see Section 1.2, the same applies hereinafter).

Neutrophil count decreased (PT Code 10029366) will be replaced by Neutropenia (PT Code 10029354), Lymphocyte count decreased (PT Code 10025256) by Lymphopenia (PT Code 10025327), White blood cell count decreased (PT Code 10047942) by Leukopenia (PT Code 10024384), and Platelet count decreased (PT Code 10035528) by Thrombocytopenia (PT Code 10043554) (the same applies hereinafter).

Data item	Data to be analyzed
Number of patients with adverse events	Number of patients experiencing adverse events
Number of adverse events	Number of adverse events observed. If the same patient has multiple occurrences of the same adverse event (PT), the total number of occurrences will be calculated.
Percentage of patients with adverse events	Is calculated using the following formula: number of patients with adverse events/number of patients included in the safety analysis set × 100.
Type of adverse events	The incidence of adverse events will be calculated by SOC and PT. For SOC, the number and percentage of patients with adverse events will be calculated. For PT, the number and percentage of adverse events will be calculated. SOCs will be presented in the internationally agreed order, and PTs will be presented in ascending order of HLGT and PT codes if their SOCs are “Investigations,” and in ascending order of PT code otherwise. If the same patient has multiple occurrences of the same adverse event (PT), the event will be counted once per patient.

(3) Figure/table number

Tables 5.1-1 to 5.1.1-3

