5.9 Analysis of items of particular interest

5.9.1 Occurrence of the adverse drug reaction of peripheral nerve disorder and infections

(1) Analysis sets to be used

Safety analysis set, safety analysis set (Hodgkin's lymphoma), and safety analysis set (anaplastic large-cell lymphoma)

(2) Data to be analyzed

The incidence of peripheral nerve disorders considered related to Adcetris will be calculated for each CTCAE grade (the worst one) by symptom of peripheral nerve disorder (peripheral sensory neuropathy, peripheral motor neuropathy, or peripheral neuropathy) and PT (see Section 1.2 for the definition of symptoms of peripheral nerve disorders). For symptoms of peripheral nerve disorders, the number and percentage of patients with peripheral nerve disorder will be calculated. For PT, the number and percentage of peripheral nerve disorder will be calculated. PTs will be presented in ascending order of PT code.

The CTCAE grade (the worst one) is higher in the order of Grades 5, 4, 3, 2, 1, and unknown. If the same patient has multiple occurrences of the same symptom of peripheral nerve disorder or the same PT, the symptom of peripheral nerve disorder or PT with the highest CTCAE grade (the worst one) will be counted for the respective category once per patient:

Data item	Category
CTCAE Grade (the worst one) for peripheral nerve disorders	Grade 1, Grade 2, Grade 3, Grade 4, Grade 5, or unknown

(3) Figure/table number

Tables 5.9.1-1 to 5.9.1-3

5.9.2 Occurrence of peripheral nerve disorders considered related to Adcetris by patient demographics and baseline characteristics and treatment given

(1) Analysis sets to be used

Safety analysis set, safety analysis set (Hodgkin’s lymphoma), and safety analysis set (anaplastic large-cell lymphoma)

(2) Data to be analyzed

For each data item of patient demographics and baseline characteristics and treatment given, patients will be stratified into the categories below, and the incidence of peripheral nerve disorders considered related to Adcetris will be calculated by CTCAE Grade (the worst one). The CTCAE grade (the worst one) is higher in the order of Grades 5, 4, 3, 2, 1, and unknown. If the same patient has multiple occurrences of the same peripheral nerve disorder (PT), the peripheral nerve disorder with the highest CTCAE grade will be counted once for the category:

Data item	Category
CTCAE Grade (the worst one) of peripheral nerve disorder	Grade 1, Grade 2, Grade 3, Grade 4, Grade 5, or unknown

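### On-treatment neuropathy is identified only from its dedicated form field, so cases recorded in another event field could be missing from the neuropathy tables

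*SAP*

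**What the plan says.** **On-treatment neuropathy.** The Definition table in Section 1.1 of the final SAP sets up three classes.
- The sensory class is "Adverse events with “Sensory neuropathy” entered in the “Category of peripheral nerve disorders” in the field of" adverse-event field [1].
- The motor class is "Adverse events with “Motor neuropathy” entered in the “Category of peripheral nerve disorders” in the field of" that same field.
- The third class is "Adverse events with “Other” entered in the “Category of peripheral nerve disorders” in the field of" the same field again. 'Other' is therefore a category inside field [1], not a collecting point for the other event fields.

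Each class receives one fixed preferred term, whatever symptom was written. Section 5.1.1 repeats this for data in field [1]: "MedDRA PT Code for peripheral sensory neuropathy, peripheral motor neuropathy, or peripheral neuropathy should be assigned, regardless of data entered in" the symptoms box. It adds that the rule holds for what follows.

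**Where it is used.** Section 5.9.1 refers the reader back: "see Section 1.2 for the definition of symptoms of peripheral nerve disorders". (In the final SAP the section numbered 1.2 is headed as display digits; the definitions stand in the table just before it.) Sections 5.9.2 to 5.9.4 and list 5.10 speak of drug-related peripheral nerve disorders and give no definition of their own. The two preceding SAP versions carry the same field rule, and neither supplemental SAP changes it.

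**Baseline.** Concurrent peripheral neuropathy is found by a MedDRA query: "Patients with a concurrent illness that falls under the category of SMQ Code 20000034", narrow scope.

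**Infusion reaction.** Its preferred term is assigned "regardless of symptoms entered in the field of “Adverse events: [4] Infusion reaction", so it is field-based too.

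**The concern.** Neuropathy comes first among the adverse events of particular interest in Protocol 9.2.5. The protocol wants its risk factors, usual time to onset, outcomes and treatment status described. Under the SAP's wording, whether a case enters the tables meant to do this depends on which box the investigator used. About 100 institutions report on paper forms (Protocol 6.0 and 7.2), so that choice may vary between sites. A case written under another event heading would show in the general tables and be missing from the neuropathy tables, and the SAP has no step that would reveal the gap.

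**Working it through.** **Step 1: how each event of interest is found in the final SAP**

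| Event of interest | Rule | Depends on the form field? |
|---|---|---|
| Peripheral nerve disorders | category entered in field [1] (Definition table; 5.1.1) | yes |
| Infusion reaction | entry in field [4] (Definition table; 5.1.1) | yes |
| Infections | MedDRA system organ class 10021881 (Definition table) | no |
| Neutropenia | preferred term, with neutrophil count decreased mapped to it (5.1.1) | no |
| Pulmonary disorders | list of preferred terms (Appendix) | no |

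The field numbers show that the form has several adverse-event fields. A neuropathy can therefore be written outside field [1], and nothing in the SAP would then bring it into the three classes.

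**Step 2: what happens to such an entry.** It keeps its own preferred term and is counted in 5.1 and 5.2, with grade, seriousness, onset and outcome. Read literally, it meets none of the three definitions. A programmer who selected on the three assigned preferred-term codes would pick it up if it happened to carry one of them, but would miss any other term in the SMQ. A patient who also has an entry in field [1] is still counted as a patient. Only patients whose neuropathy is recorded solely elsewhere disappear from the patient counts.

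**Step 3: possible size, as illustration only.** The SAP gives no figure on this point. Inputs:
- N = 140 patients (Protocol 3.1). This reproduces from the plan's own rationale: the exact binomial chance of at least 10 infusion reactions at 11% is 0.9518 with n = 140 and 0.9490 with n = 139.
- p = 56%, the neuropathy frequency in the two pooled non-Japanese phase 2 studies (Protocol 3.2).
- m = share of affected patients recorded only outside field [1]. This is an assumption; the range shown is 0% to 20%.

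Reported rate = p × (1 − m). Patients missed = N × p × m, where N × p = 140 × 0.56 = 78.4.

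| m | Reported rate | Patients missed |
|---|---|---|
| 0% | 56.0% | 0 |
| 5% | 53.2% | 3.9 |
| 10% | 50.4% | 7.8 |
| 20% | 44.8% | 15.7 |

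For scale, 78 of 140 is 55.7%, with an exact 95% interval of 47.1% to 64.1%, a half-width of (64.1 − 47.1)/2 = 8.5 points. The shifts at 5% and 10% (2.8 and 5.6 points) are smaller than that. The shift at 20% (11.2 points) is larger.

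**The case against.** The case on the other side is substantial.

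- The form and its query rules are not in the documents. Field [1] is dedicated to neuropathy and has an 'Other' category, so every neuropathy has a natural place there. Nothing shows that any was entered elsewhere.
- Infusion reaction is handled in the same way. Using the investigator's classification for both events looks like a deliberate choice that stops one clinical entity from scattering over many symptom terms.
- No event is lost from the study; the general tables keep it.
- Only 5.9.1 cites the field definition outright. For 5.9.2 to 5.9.4 and 5.10 it applies through the carry-forward in 5.1.1 and the absence of any alternative.

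All of this stands. It limits the likely size and explains the design, but it does not supply a check of the other fields.

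A reader might also infer more than the documents support:

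- **That incidence can only be understated.** Entries outside field [1] can only lower the count, but the field rule also overrides the written symptom. It can therefore include events that a term-based query would not.
- **That the field rule is narrower than the SMQ.** Field [1] accepts any symptom, while the SMQ is limited to narrow scope. The documents do not show either set contained in the other.
- **That 5.9.2 sets a query-based baseline status against a field-based outcome.** The factor in 5.9.2 is graded from none to Grade 4. The SMQ gives only presence or absence, so the grade needs another source, which the SAP does not name. A baseline covariate need not be measured by the same rule as the outcome in any case.
- **That 56% is the true rate for these tables.** Sections 5.9.1 to 5.9.4 and 5.10 count drug-related events. Protocol 3.2 does not say that its 56% is restricted in that way.

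**Conclusion.** The gap is real but modest. The neuropathy tables depend on one form field, while three of the other four events of interest are found by coded term wherever they were written. Neuropathy recorded elsewhere could be absent from 5.9.1 to 5.9.4 and 5.10 and so lower those counts. The documents do not allow the number to be estimated, and it may be zero. The loss of up to about 16 of 140 patients rests entirely on an assumed share of 20% and on borrowing the 56%. This is a worthwhile low-cost improvement, not evidence that the results are wrong.

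**What to change.** Keep the field [1] definition and its class assignment. Add to it any event in another adverse-event field whose preferred term falls in SMQ 20000034, narrow scope, in MedDRA 19.1 (the version fixed in SAP 1.6). Assign added events to the sensory or motor class where the term says so, and otherwise to the class 'Peripheral neuropathy'. Use the combined definition in 5.9.1 to 5.9.4 and 5.10, and report how many events and how many patients the addition brings in, so that the field-based result stays visible.

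There is a precedent: Supplemental SAP 2 restated neutropenia by preferred term, added febrile neutropenia and repeated those tables. The cost is one changed definition, one query on data already coded, and a class review of a few events. If a form rule already moves such entries into field [1], the query should add nothing and the SAP can say so.
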